9.3 Analysis Methods

Analysis methods for clinical end points, described in detail below, are summarized in Table 9-1.

Table 9-1 Table of Efficacy Variables and Analysis Methods

Endpoint (section reference)	Analysis Technique (section reference)	Analysis Sample
Primary		
Proportion of subjects who are successfully withdrawn from immunosuppression ‡	Proportion with exact 95% confidence interval	PP1, PP2
Secondary		
1) Immunosuppression-free duration	Median Time and 95% CI	All subjects completing withdrawal
2) Time to Rejection	Median Time and 95% CI	PP1
3) Graft Loss or Death	Proportion with exact 95% confidence interval	PP1, PP2

‡ Defined as those who remain off immunosuppression for at least 1 year.

9.3.1 Primary Efficacy Analyses

The proportion of subjects in the PP1 and PP2 samples who are successfully withdrawn will be descriptively summarized with 95% confidence intervals using an exact binomial method.

9.3.2 Secondary Efficacy Analyses

- 1) Median immunosuppression-free duration will be estimated for all subjects completing withdrawal. Duration will be displayed graphically with a Kaplan-Meier curve and the corresponding median and two-sided 95% confidence interval.
- 2) Median time from initiation of immunosuppression withdrawal to first episode of acute rejection or to first diagnosis of chronic rejection will be estimated for the PP1 sample. Duration will be displayed graphically with a Kaplan-Meier curve and the corresponding median and two-sided 95% confidence interval.
- 3) The proportion of subjects experiencing graft loss or death after initiation of immunosuppression withdrawal will be descriptively summarized for the PP1 and PP2 samples as well as the ITT sample with 95% confidence intervals using an exact binomial method.

9.4 Examination of Subgroups

No subgroup analyses are planned.

10. SAFETY EVALUATION

10.1 Overview of Safety Analysis Methods

All safety analysis will be carried out using the PP1 sample and the PP2 sample defined in Section 5 unless otherwise noted. Missing safety information will not be imputed. These analyses will not be stratified by site. Safety will be analyzed through the reporting of adverse events, vital signs, physical examinations, and changes in routine laboratory values.

Listings will be prepared for all safety measurements. All listings will be sorted in order of subject ID and time of assessment (e.g., visit, time, and/or event).

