### 4.2 INCLUSION CRITERIA

1. Living-donor liver transplantation from a parental donor.
2. Age less than 18 years at the time of transplantation.
3. At least 4 years since transplantation.
4. Availability and willingness of parental liver donor to participate in the trial.
5. Liver biopsy at screening demonstrating no evidence of acute or chronic rejection and a less than stage 2 fibrosis on the Ishak scale.
6. Negative urine pregnancy test at entry and agreement to use a medically acceptable form of birth control during the study for women of childbearing potential.
7. Negative purified protein derivative (PPD) test results or history of appropriate treatment.

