## 8.3 COLLECTING ADVERSE EVENTS

### 8.3.1 Methods of Collection

Adverse events will be collected from the time consent is obtained from the participant until the time the event resolves or until he/she completes study participation, whichever comes first.

Adverse events may be discovered by any of these methods:

- Observing the participant.
- Questioning the participant in an objective manner.
- Receiving an unsolicited complaint from the participant.

An abnormal value or result from a clinical or laboratory evaluation (e.g., a radiograph, an ultrasound, or an electrocardiogram) can also indicate an adverse event if it is determined by the investigator to be clinically significant. If this is the case, it must be recorded in the source document and as an adverse event on the appropriate adverse event form(s). The evaluation that produced the value or result should be repeated until that value or result returns to normal or can be explained and the participant’s safety is not at risk.

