### 8.3.2 Collecting Serious Adverse Events

Serious adverse events will be collected from the time the participant begins study participation until 30 days after he/she completes or prematurely withdraws from the study.

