#### **9.2.2 Analysis of Secondary Endpoints**

##### **9.2.2.1 Safety of Immunosuppression Withdrawal**

The following endpoints will be analyzed using the PP and ITT samples:

- The proportion of participants who have graft loss or who die after initiation of immunosuppression withdrawal will be descriptively summarized with a two-sided, 95% CI.
- Median time from initiation of immunosuppression withdrawal to first episode of acute rejection or to first diagnosis of chronic rejection, with a corresponding two-sided 95% CI, will be estimated using the Kaplan-Meier method.
- Distribution of severity among rejection episodes and the incidence of adverse events will be descriptively summarized using frequency tables with enumerations and percentages.
- Descriptive statistics (mean, standard deviation, mean change from baseline) for renal function, blood pressure, cholesterol level, and glucose control over time will be presented.

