5. ANALYSIS POPULATIONS

Intent to treat (ITT) sample will be defined as all subjects who have signed informed consent and are enrolled. For the purpose of these analyses enrollment is defined as beginning the screening process for participation in the study.

Per protocol (PP) samples will be defined as all subjects in whom immunosuppression withdrawal is attempted.

- Per protocol 1 (PP1) sample will be defined as all subjects in whom immunosuppression withdrawal is attempted.
- Per protocol 2 (PP2) sample will be defined as all subjects without inclusion/exclusion criteria protocol deviations in whom immunosuppression withdrawal is attempted.

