10.3 Adverse Events

All adverse events will be coded using the MedDRA dictionary, including classification by system organ class (SOC) and preferred term. The severity of adverse events (AE) will be classified using the National Cancer Institute's Common Toxicity Criteria for Adverse Events toxicity scale.

An overall summary table will be developed to report the number of events and the number and percentage of subjects having at least one event in the following categories:

- Adverse events (AEs)
- Serious Adverse Events (SAEs)
- Deaths
- AEs reported as definitely, probably, or possibly related to immunosuppression withdrawal
- AEs reported by severity

The tabulations described above will not include classifications by SOC and preferred term.

In addition, a summary table of adverse events classified by MedDRA SOC and preferred term will be provided for each of the following:

- AEs
- AEs by maximum severity
- AEs by relationship to immunosuppression withdrawal.

The summary tables will present the total number of events as well as the number and percentage of subjects experiencing the events by clinical phenotype. When reporting the number of AEs, if the same AE occurs for a subject on multiple occasions the event will be counted once for each occurrence. When reporting the number of subjects experiencing the events, a subject will only be counted once if they ever experience an event within the particular system organ class or preferred term. Percentages will be based on the number of subjects categorized in each clinical phenotype.

Separate data listings will be provided for all AE and AEs leading to treatment discontinuation/study termination ordered by subject id.

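### Screening-biopsy complications in children who never start withdrawal would appear only in listings, because the SAP limits adverse-event tables to PP1 and PP2

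*SAP*

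**What the plan says.** SAP 10.1 gives the default for safety: "All safety analysis will be carried out using the PP1 sample and the PP2 sample defined in Section 5 unless otherwise noted". SAP section 5 says who that is: "Per protocol 1 (PP1) sample will be defined as all subjects in whom immunosuppression withdrawal is attempted". PP2 is the part of PP1 without eligibility deviations. SAP 10.3 names no other sample for adverse events, and its tables are split by tolerant and not-tolerant phenotype: "Percentages will be based on the number of subjects categorized in each clinical phenotype". SAP 10.4.1 handles serious adverse events the same way and adds displays of deaths, again without naming a sample. Elsewhere the SAP does name ITT: for Banff grade (10.4.2), for renal function, blood pressure, cholesterol and glucose (10.4.5), and for graft loss or death after withdrawal begins (9.3.2).

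Protocol 9.2.2.1, whose list includes the incidence of adverse events, says: "The following endpoints will be analyzed using the PP and ITT samples". Protocol 9.1 defines ITT as consented and enrolled. The documents differ on what enrolled means. Protocol 3.6 dates enrollment from the day withdrawal starts, but SAP section 5 says: "For the purpose of these analyses enrollment is defined as beginning the screening process for participation in the study".

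The biopsy is an eligibility condition (protocol 4.2, item 5): "Liver biopsy at screening demonstrating no evidence of acute or chronic rejection and a less than stage 2 fibrosis on the Ishak scale". It takes place at visit -1, up to 2 weeks before visit 0 or on the same day (protocol 6.1). On collection, protocol 8.3.1 says: "Adverse events will be collected from the time consent is obtained from the participant until the time the event resolves". Protocol 8.3.2 says: "Serious adverse events will be collected from the time the participant begins study participation until 30 days after he/she completes or prematurely withdraws".

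**The concern.** The screening biopsy is an invasive procedure that the protocol requires. Protocol 6.5.1 asks for at least 4 cm of core. One centimetre goes to formalin histology, and the rest to lymphocyte, gene-expression and immunohistochemical work. A child who is biopsied and then found ineligible carries that risk without a chance to stop immunosuppression.

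Under the SAP's sample rule, the tables would describe biopsy harm only in children who went on to start. That selection may not be neutral, since a serious complication could itself be the reason a child does not start.

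There is a related gap among starters. Protocol 8.4.2 attributes events to study participation, whereas SAP 10.3 tabulates relatedness to immunosuppression withdrawal. A biopsy complication has no natural row there.

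**Working it through.** **Step 1. Who is in which sample.**

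| Child | SAP ITT (section 5) | Protocol ITT, read with 3.6 | PP1, PP2 | AE, SAE and death tables (SAP 10.3, 10.4.1) |
|---|---|---|---|---|
| Fails at visit -2, not biopsied | yes | no | no | no |
| Biopsied at visit -1, never starts | yes | no | no | no |
| Starts withdrawal | yes | yes | PP1 yes; PP2 if no eligibility deviation | yes |

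The second row is the group at issue.

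**Step 2. Whether another ITT output would show the event.** Banff grade describes rejection episodes. SAP 10.4.5 covers renal function, blood pressure, cholesterol and glucose. Graft loss or death in 9.3.2 counts only events after withdrawal begins. None of these would show a biopsy complication in a child who never starts. SAP section 14 records no change from protocol 9.2.2.1 for adverse-event incidence.

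**Step 3. What remains.** SAP 10.1 promises listings of all safety measurements, 10.3 lists all adverse events, 10.4.1 lists serious adverse events and deaths, and 10.4.6 lists infections for all subjects. None of these sentences restricts the listing to PP1. The event is visible there, but without a denominator.

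**Step 4. Illustration of size.** The plan states no figure on this point. The interval method was checked on its sample-size examples: the exact 95% interval is 23.1% to 68.5% for 9/20 and 5.7% to 43.7% for 4/20, both as printed in protocol 9.3 and SAP 3.7.

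Assume 20 starters (the planned number), m biopsied non-starters and a complication risk r per child. Only the 20 comes from the documents. The share of biopsied children outside the tables is m/(20 + m). The chance that at least one complication goes untabulated is 1 - (1 - r)^m.

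| m | Share outside tables | r = 1% | r = 3% | r = 5% |
|---|---|---|---|---|
| 2 | 2/22 = 9.1% | 2.0% | 5.9% | 9.8% |
| 5 | 5/25 = 20.0% | 4.9% | 14.1% | 22.6% |
| 10 | 10/30 = 33.3% | 9.6% | 26.3% | 40.1% |
| 20 | 20/40 = 50.0% | 18.2% | 45.6% | 64.2% |

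For example, m = 10 and r = 3% gives 1 - 0.97^10 = 26.3%.

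**Step 5. What a reader of the tables would see.** Suppose the only complication is in a non-starter. PP1 shows 0/20 (exact 95% CI 0 to 16.8%). A table of all biopsied children shows 1/22 = 4.5% (0.1% to 22.8%) if m = 2, and 1/40 = 2.5% (0.1% to 13.2%) if m = 20. The intervals overlap widely. What changes is that an event that occurred is counted.

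**The case against.** The strongest reply is that little is lost. The events are in the listings, and in a study of about 20 children a listing shows a single complication clearly. Serious events go to the safety centre within 24 hours (protocol 8.5.1), and the DSMB receives listings of all of them (8.5.3). This stands, and it limits the point to summary tables and denominators. Listings still do not supply what protocol 9.2.2.1 describes, which is frequency tables with counts and percentages.

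A second reply is that adverse-event incidence sits under the safety of withdrawal, for which children who attempted withdrawal are the natural sample. That is a good reason to leave the PP1 and PP2 tables alone and put the biopsy events in a separate table.

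Four stronger readings are tempting, and the documents do not support them:

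- **That the SAP removed these children from a sample in which the protocol clearly had them.** Under protocol 3.6, enrollment begins when withdrawal starts, so the protocol's ITT may hold starters only. That reading makes ITT almost the same as PP and the separate ITT analyses redundant, but it cannot be ruled out. Only the SAP's ITT clearly includes non-starters.
- **That every candidate is biopsied.** Screening has two steps. Serology, autoantibodies, chemistry and GFR come at visit -2, and the biopsy follows at visit -1, so a child who fails earlier need not have one.
- **That serious events before withdrawal go uncollected.** Protocol 8.3.2 starts at the beginning of study participation, which is undefined. Protocol 8.3.1 starts at consent, and 8.2.2 requires any event meeting a serious criterion to be reported as such. The wording differs, but it shows no gap in collection.
- **That the size is known.** It rests on assumed inputs.

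**Conclusion.** The point holds as a gap in summary reporting. With SAP 10.1, 10.3 and 10.4.1 followed as written, a child harmed by the screening biopsy who never starts withdrawal is in no adverse-event, serious-adverse-event or death table. This is so although the protocol plans adverse-event incidence in ITT and the SAP's own ITT runs from screening.

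The conclusion follows from the sample definitions and needs no assumed number. Its size does: across 2 to 20 biopsied non-starters and a risk of 1% to 5%, the chance of at least one untabulated complication is 2% to 64%, and neither input has a source in the documents. Selective exclusion is plausible but undocumented. The primary endpoint and the withdrawal results are unaffected. The change should be made because it is cheap and gives a denominator to harm from a required invasive procedure in children.

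**What to change.** 1. In SAP 10.3 and 10.4.1, add one separate table of adverse events and serious adverse events from consent to the start of withdrawal, with biopsy-related events shown by seriousness. Because withdrawal may begin on the day of the biopsy, say how a screening-biopsy event that begins after visit 0 is counted.
2. Use as denominator all consented children who actually had the screening biopsy. The whole SAP ITT would not do, because it includes children who failed before biopsy and would dilute the rate.
3. Give non-starters their own column or an overall column. The 10.3 tables are split by phenotype, and these children should not be counted as not tolerant.
4. Leave the PP1 and PP2 withdrawal tables unchanged, and state that the adverse-event listings cover all consented children.
5. Reconcile the definitions of enrollment in protocol 3.6 and SAP section 5, and the start-of-collection wording in protocol 8.3.1 and 8.3.2.

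The cost is one extra table and wording changes in both documents. Protocol 8.3.1 already calls for collection from consent, so no new assessments are needed.

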10.2 Extent of Exposure

The displays that are used to describe the total burden of immunosuppression and treatment compliance (detailed in section 8 and 9.2.2) will also be used to assess treatment exposure.

10.3 Adverse Events

All adverse events will be coded using the MedDRA dictionary, including classification by system organ class (SOC) and preferred term. The severity of adverse events (AE) will be classified using the National Cancer Institute's Common Toxicity Criteria for Adverse Events toxicity scale.

An overall summary table will be developed to report the number of events and the number and percentage of subjects having at least one event in the following categories:

- Adverse events (AEs)
- Serious Adverse Events (SAEs)
- Deaths
- AEs reported as definitely, probably, or possibly related to immunosuppression withdrawal
- AEs reported by severity

The tabulations described above will not include classifications by SOC and preferred term.

In addition, a summary table of adverse events classified by MedDRA SOC and preferred term will be provided for each of the following:

- AEs
- AEs by maximum severity
- AEs by relationship to immunosuppression withdrawal.

The summary tables will present the total number of events as well as the number and percentage of subjects experiencing the events by clinical phenotype. When reporting the number of AEs, if the same AE occurs for a subject on multiple occasions the event will be counted once for each occurrence. When reporting the number of subjects experiencing the events, a subject will only be counted once if they ever experience an event within the particular system organ class or preferred term. Percentages will be based on the number of subjects categorized in each clinical phenotype.

Separate data listings will be provided for all AE and AEs leading to treatment discontinuation/study termination ordered by subject id.

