### 8.4.2 Attribution Definitions

The relation, or attribution, of an adverse event to study participation will be determined by the site investigator. The site investigator will also record the determination of attribution on the appropriate CRF and/or SAE reporting form. The relation of an adverse event to study participation will be determined using the descriptors and definitions provided in Table 6.

For additional information and a printable version of the NCI-CTCAE manual, consult the NCI-CTCAE web site: <http://ctep.cancer.gov/reporting/ctc.html>.

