**Table 6. Attribution of adverse events**

Code	Descriptor	Definition
Unrelated Category		
1	Unrelated	The adverse event is clearly not related to study participation.

Related Categories		
2	Unlikely	The adverse event is doubtfully related to study participation.
3	Possible	The adverse event may be related to study participation.
4	Probable	The adverse event is likely related to study participation.
5	Definite	The adverse event is clearly related to study participation.

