### **9.4.5 Safety**

All adverse events, including infections, malignancies, morbidity, and side effects associated with immunosuppression withdrawal and/or study participation, will be classified by body system and preferred term according to the *Medical Dictionary for Regulatory Activities* (MedDRA).

Frequency tables by category of event (e.g., serious, related to study participation, causing the discontinuation from the study) and by NCI-CTCAE grade will be presented. Laboratory values and vital signs will also be summarized by mean, standard deviation, and change from baseline.

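### The SAP tabulates adverse events by relation to immunosuppression withdrawal, but the only attribution the protocol describes is to study participation

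*SAP*

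**What the plan says.** **Protocol.** Section 8.4.2 makes the site investigator responsible for attribution and names one object for it: "The relation of an adverse event to study participation will be determined using the descriptors and definitions provided in Table 6". All five definitions in Table 6 are worded that way. Code 5, Definite, reads "The adverse event is clearly related to study participation". Code 2, Unlikely, reads "The adverse event is doubtfully related to study participation" and stands under the heading for related categories. Section 9.4.5 plans "Frequency tables by category of event (e.g., serious, related to study participation, causing the discontinuation from the study" as table categories. Section 8.3.1 sets the start of collection: "Adverse events will be collected from the time consent is obtained from the participant".

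**SAP.** Section 10.3 puts "AEs reported as definitely, probably, or possibly related to immunosuppression withdrawal" in the overall summary table and "AEs by relationship to immunosuppression withdrawal" among the tables by system organ class and preferred term. Section 10.4.1 handles serious events in the same manner. Section 10.1 bases the safety analyses on the PP1 and PP2 samples, which section 5 defines by whether withdrawal was attempted.

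**The concern.** The SAP keeps the protocol's descriptors (definite, probable, possible) but changes what they describe. Study participation, read naturally, includes percutaneous liver biopsies and blood draws as well as the taper. A bleed after a protocol biopsy could properly be coded as definitely related to participation, and the SAP table would then show it as definitely related to withdrawal.

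Safety of withdrawal is a secondary objective (Protocol 2.2.1), and the trial has no control arm. Attribution is therefore one of the few ways a reader can separate possible harm from withdrawal from harm due to study procedures. A table headed with the wrong relation answers a question that, on the text, the sites were not asked.

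**Working it through.** The plan gives no figure on this point, so the check is a comparison of text.

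1. **What is collected.** Protocol 8.4.2 and Table 6 describe a single code from 1 to 5 for relation to study participation. Neither document describes a second attribution to withdrawal.

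2. **What is reported.** Both relatedness displays in SAP 10.3 refer to withdrawal, and SAP 10.4.1 extends them to serious events. The SAP gives no rule for deriving this relation from the Table 6 code. SAP section 14, on changes from the protocol analyses, does not list the switch.

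3. **Are the two terms the same?** Protocol 9.4.5 names them side by side as separate possible sources of side effects, joined by and/or, so the protocol itself does not treat them as synonyms. Protocol 6.5 also schedules biopsies at screening and, for children who stay off drug, for years afterwards. These belong to participation but are not steps of the taper.

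4. **Can an event precede withdrawal and still be counted?**
   - Collection starts at consent (Protocol 8.3.1), and the schedule of events records adverse events at visit -1, the screening biopsy visit.
   - Withdrawal starts at visit 0, on the day of that biopsy or up to 2 weeks later (Protocol 6.1).
   - PP1 and PP2 restrict which subjects are counted, not which event dates. SAP 10.3 sets no onset limit, whereas SAP 12.1 does classify medications against the date withdrawal began.
   - So a complication of the screening biopsy can enter the table if the child later starts withdrawal. Screen failures are outside PP1 and PP2 and do not enter.

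5. **Which codes count as related?** Table 6 places codes 2 to 5 under its related heading. The related row of the SAP summary takes definite, probable and possible, which are codes 3 to 5. An event coded Unlikely is therefore related by the Table 6 heading and not related in the SAP row.

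**The case against.** **The form is unseen.** Protocol 8.4.2 says attribution is recorded on the case report form or the serious event form, and the SAP speaks of events reported as related to withdrawal. A form that asks about withdrawal would mean no event is misclassified and only the protocol wording needs correction. This stands: the mismatch in wording is certain, but the miscounting is conditional.

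**Study participation is not defined.** That it covers procedures is a natural reading, not a stated one. Serious events are collected from when participation begins (Protocol 8.3.2), so it is also unclear whether a serious event at screening is captured. This limits how firmly the point about events before withdrawal can be put, mainly for serious events. Other adverse events are collected from consent.

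**No endpoint is affected.** The safety endpoints are graft loss or death, time to rejection, histologic severity, incidence of all adverse events, and renal and metabolic change. None uses attribution. With 20 participants, the listings and subject profiles would also let a careful reader identify a bleed after biopsy. This stands and limits the importance, but the summary table would still carry a label that the protocol does not support.

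**The cut-off is minor.** The SAP states its own cut-off, and the protocol's grouping is only a table heading. This is largely fair. Showing every category settles it.

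**Conclusion.** As written, SAP 10.3 and 10.4.1 report a relation that neither document says is collected or derived. If the case report form has no separate withdrawal field, events that sites attributed only to participation would be tabulated as related to withdrawal. For children who start withdrawal, these could include events with onset before visit 0.

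The size cannot be computed because the documents give no complication rate. No defined safety endpoint changes.

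A reader might go further and infer that procedure complications would pile up in the tolerant column, since a child who stays off drug has 5 protocol biopsies under Protocol 6.5 (screening plus four). The documents do not support that. For-cause biopsies, which may fall mostly on children who fail withdrawal, are not counted. The SAP's own schedule ends at L24 and contains 4 (visit -1, visit 12, M24, L24). Tolerant status needs only one year off drug, so some tolerant children will have fewer. Under the protocol's example of 9 successes in 20, one affected tolerant child is 1/9 = 11.1% of that column, but this is the weight of any one child and does not measure the error.

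**What to change.** 1. In SAP 10.3 and 10.4.1, label the tables *related to study participation*, to match Table 6 and Protocol 9.4.5. If the case report form does hold a separate attribution to withdrawal, cite that field in the SAP and align Protocol 8.4.2, Table 6 and 9.4.5 with it.
2. Tabulate events with onset before visit 0 separately from those with onset on or after it.
3. Show all five Table 6 categories in the relationship table, so that the reader can see where Unlikely falls.

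This does not require anyone to sort events afterwards into procedure-related and other; that would add an open-label judgement the investigator never made.

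The change needs SAP wording and the existing attribution codes, event onset dates and visit 0 dates. It needs no new data and does not affect participant care. The downside is slightly longer adverse event tables.

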### 8.5.2 Options for Reporting Serious Adverse Events

After the SAE has been assessed by the investigator, there are three options for reporting an event to the appropriate health authorities:

- **No requirement to report.** This option applies if the adverse event is deemed not serious by the Rho Fed Safety PSS, the ITN clinical physician and the NIAID medical monitor.
- **Standard reporting is required.** This option applies if the adverse event is classified as one of the following: (a) serious, expected, and study related; (b) serious, expected, and not study related; or (c) serious, unexpected and not study related.
- **Expedited reporting is required.** This option applies if the adverse event is considered serious, unexpected, and study related. These events must be reported by the sponsor to the appropriate health authorities within 15 days; fatal or life-threatening events must be reported within 7 days. For expedited SAEs, all sites must attach the notification letter and MedWatch/CIOMS to the current investigator's brochure.

All investigators must report serious adverse events to their respective IRBs as mandated by them.

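### The SAP's related-event row leaves out 'Unlikely', which Protocol Table 6 classes as related, so its related AE and SAE counts can fall short of the protocol's definition

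*SAP*

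**What the plan says.** **Protocol.** Section 8.4.2 makes Table 6 the attribution scale: "The relation of an adverse event to study participation will be determined using the descriptors and definitions provided in Table 6". Table 6 puts a single code in its unrelated category, code 1, defined as "The adverse event is clearly not related to study participation". The other four codes stand under the heading "Related Categories". The lowest of them is code 2, Unlikely, defined as "The adverse event is doubtfully related to study participation". Section 9.4.5 plans frequency tables by category of event and gives relation to study participation as one example of a category. It sets no cut of its own, so Table 6 is the only place where the protocol divides related from unrelated.

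**SAP.** The overall summary table in section 10.3 has one row for relatedness: "AEs reported as definitely, probably, or possibly related to immunosuppression withdrawal". The same section plans a table by system organ class and preferred term of "AEs by relationship to immunosuppression withdrawal", without saying which levels it will show, and a listing of all AEs. Section 10.4.1 applies the section 10.3 approach to SAEs. Section 14, which is headed as the place for changes to the protocol's planned analyses, lists no change to the definition of related.

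**The concern.** Both documents group events by relatedness, and they draw the line at different places. An event that the investigator codes 2 is related under the protocol's table and falls outside the SAP's related row. The SAP does not say that it departs from Table 6, so someone who takes the definition from the protocol and the number from the final report will combine two different cuts.

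The mismatch runs one way only: the SAP row can equal the protocol-defined count or be lower, never higher. Safety of withdrawal is a secondary objective, and the trial has one arm of 20 participants with no control rate, so readers may lean on investigator attribution when they interpret the events. What is at stake is the accuracy of one reported safety count for AEs and the matching one for SAEs.

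**Working it through.** The documents state no figure on this point, and no sample-size or error-rate formula applies. The check is a comparison of codes.

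| Table 6 code | Descriptor | Protocol Table 6 | SAP 10.3 summary row |
|---|---|---|---|
| 1 | Unrelated | unrelated | not counted |
| 2 | Unlikely | **related** | **not counted** |
| 3 | Possible | related | counted |
| 4 | Probable | related | counted |
| 5 | Definite | related | counted |

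**Events.** Let n2, n3, n4 and n5 be the numbers of events with each code.

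- Protocol-defined related count = n2 + n3 + n4 + n5.
- SAP row = n3 + n4 + n5.
- Shortfall = n2, which is zero or more.

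The same subtraction applies to SAEs under SAP 10.4.1.

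**Subjects.** The SAP also reports the number and percentage of subjects with at least one event. That number falls short by the subjects who have a code 2 event and no event coded 3 to 5. A subject with both kinds is counted either way.

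**Scale per subject, for illustration.** The documents give neither n2 nor the number of such subjects, so only the effect of one subject can be shown.

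- All 20 participants as denominator: 1/20 = 5 percentage points.
- SAP 10.3 bases percentages on the number in each clinical phenotype. Protocol 9.3 uses 4 of 20 and 9 of 20 successes as examples. One such subject in the tolerant group would move that group's percentage by 1/4 = 25 points or 1/9 = 11.1 points.

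These are step sizes caused by small denominators. They do not estimate how often the situation will arise.

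**What the row feeds.** The secondary endpoint is the incidence of adverse events, with no filter on attribution (Protocol 3.3.2.1, SAP 3.2.2). The primary endpoint is time off immunosuppression of at least 1 year. The specific stopping rules in Protocol 3.5.2 and 3.5.3 turn on death, graft loss, types of rejection and their treatment. None of these uses a Table 6 code.

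**The case against.** The best defence is that the SAP row hides nothing. It names the three levels it counts, so a careful reader can see that Unlikely is out. The by-relationship table and the full AE listing may still show code 2 events, and all AEs, SAEs, deaths and severities are tabulated regardless of attribution. Counting possible-or-higher is also a reasonable analytic choice, since it keeps doubtfully attributed events out of the headline figure. In addition, Table 6 attributes events to study participation while the SAP row refers to immunosuppression withdrawal, so the two counts differ in wording as well as in codes.

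Most of this stands, and it limits the consequence. It does not remove the mismatch. The protocol placed Unlikely among the related codes, the SAP uses a narrower cut without recording it, and the levels of the by-relationship table are undefined, so the narrower grouping could be carried over there.

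Two stronger readings are tempting and are not supported:

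- A reader might infer that the final tables will disagree with related counts given to the DSMB or health authorities. Protocol 8.5.3 gives the DSMB listings of all SAEs, plus notice of expedited ones; the documents describe no related-event count sent to it. Expedited reporting under Protocol 8.5.2 covers a subset: "This option applies if the adverse event is considered serious, unexpected, and study related". That subset would not match a table of all related events under either cut. Section 8.5.2 also does not cite Table 6, so treating code 2 as study related there is a reasonable inference and not a stated rule.
- A reader might infer a material undercount that makes withdrawal look safer overall. The documents give no frequency of Unlikely codes, so no percentage can be attached, and the main safety displays do not depend on this row.

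**Conclusion.** The inconsistency is real and minor. The SAP's related AE and SAE counts omit code 2, which Table 6 classes as related, and so fall below the protocol-defined counts by exactly the number of events coded Unlikely. That number cannot be estimated from the documents and may be zero.

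The conclusion rests on two assumptions: that the SAP's level names correspond to the Table 6 descriptors, and that the attribution recorded by sites under Protocol 8.4.2 is what feeds the SAP row. The documents offer no other scale. The point concerns how one safety category is reported.

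**What to change.** In SAP sections 10.3 and 10.4.1:

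1. Define the related row as Table 6 codes 2 to 5.
2. Keep the present possible-or-higher count (codes 3 to 5) as a second, labelled row.
3. State that the by-relationship tables show all five codes separately.

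Leave Table 6 as it is. Moving Unlikely to the unrelated category would also make the documents agree, but it could narrow the set of events read as study related for expedited reporting under Protocol 8.5.2, which is too large a side effect for a table-labelling problem.

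The cost is a short SAP edit and one extra table row. The related-event figure may become slightly less favourable. No additional data are needed, because sites already record attribution on the Table 6 scale.
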